4.2.6. Interim Contacts and Visits

Interim contacts and visits (those between regularly scheduled follow up visits) may be performed at participant request or as deemed necessary by the investigator or designee at any time during the study. All interim contacts and visits will be documented in participants' study records and on applicable CRFs. Some interim visits may occur for administrative reasons. For example, the participant may have questions for study staff. Interim visits at which no data are collected are not documented on CRFs. Other interim contacts and visits may occur in response to AEs experienced by study participants or if an STI is identified during laboratory testing after a participant's visit. When interim contacts or visits are completed in response to participant reports of AEs, study staff will assess the reported event clinically, record the event on the CRF, and provide or refer the participant to appropriate medical care.

4.2.7. Remote Visits

In response to the COVID19 pandemic, study visits may be conducted remotely. Prior to remote visits, staff will confirm with participants whether or not they wish to proceed with remote visits. Participants may be supplied with HIV self-test kits and urine pregnancy test kits and instructions for use at an in-person visit or via delivery. Study staff will confirm readiness for remote visits by phone to ensure participant safety and confidentiality. Remote visit procedures will be detailed in a standard operating procedure. PrEP may be delivered to participants at their homes following successful assessment by a clinician over the phone and following review of self-test results. Data will be collected during the in-depth interviews and short questionnaires on the feasibility and acceptability of remote visit procedures. Where it is not possible to complete all visit procedures remotely, this will be noted as a protocol deviation. Missed procedures may be completed at subsequent in person visits.

4.3. Qualitative data collection

The use of qualitative methods that give young women the opportunity to discuss their PrEP adherence barriers and facilitators in their own words and their experiences with the different interventions will result in a more culturally-sensitive approach to the study of PrEP adherence strategies among young women in Africa. Interviews will be conducted with a purposive sample of approximately 25 women and will include:

1. Young women who accept and adhere to PrEP (when possible these women will be selected based on drug levels at month 2).
2. Young women who have low drug levels at 2 months.

We will conduct interviews with samples of participants from each of the four possible interventions (two-way SMS messages, WhatsApp support groups, drug-level feedback, and monthly visits). These in-depth qualitative interviews will occur at three visits. The first will be after the month 2 visit. The second will be after their month 6 visit. The third will be after the month 9 visit or study exit. The first interview will explore the decision to take PrEP, barriers and facilitators to PrEP adherence, and experiences with either the SMS messages or the WhatsApp support groups within the first 2 months of PrEP use. This interview will also assess how women incorporated daily pill-taking into their daily routines, where they stored product, whether they disclosed their PrEP use with family members, peers, and their partner(s), whether they experienced side effects and/or other barriers to pill-taking and how that influenced their adherence in the first 2 months, and whether their risk perception and motivation to use PrEP changed over the first 2 months of use. Finally, the interview will assess their opinions about receiving and responding to SMS messages, satisfaction with support received through the WhatsApp groups, technical issues with SMS and WhatsApp messages, influence of the SMS and WhatsApp groups on their PrEP use, and concerns about message privacy and disclosure.

The second interview will further explore barriers and facilitators to PrEP adherence, and will include a discussion of participant's reaction to second randomization and allocation to counseling about their TFV results or monthly visits with special adherence counseling, as applicable.

In the final interview, research staff will ask women to provide a narrative history and timeline of their sexual relationships, living conditions, and other important factors in their lives over the prior 9 months.

Interview guides will be developed using reviews of local literature and youth community advisory board (YCAB) feedback. A primary purpose of this iterative process is developing language with which to ask questions that are accessible to informants and that encourages rather than discourages expression of responses in their own terminology.⁷³² At the end of this process, the research staff will be well-versed on the structure of the interview and the appropriateness of probes of differing detail. The semi-structured qualitative interview guide will provide a general structure for discussion but require participants to provide their own definitions of risk, motivations to use PrEP, and adherence. Participants will first be asked to discuss their general experiences with PrEP as well as medications in general. They then will be guided through an in-depth exploration of barriers and facilitators to PrEP adherence and feelings about the study interventions using a socio-ecological framework to guide initial areas of inquiry. Local researchers/ethnographers will conduct all qualitative interviews with oversight from the protocol team and approximately one social scientist. All interviews will be audio-recorded and transcribed and translated into English by trained site staff.

When conducting a qualitative exploration, the sampling method should be designed to include a range of possible perspectives on the phenomenon under study, thus ideal qualitative samples are purposive in nature. The proposed study will utilize a stratified purposive sample, which will allow for consideration of the concepts of range, saturation/redundancy, and stratification in the sampling frame.⁷⁴³ We also took into account feasibility when creating our sample sizes, a factor that is especially relevant in qualitative research with “hard-to-reach” populations such as youth. We will stratify the sample based on PrEP adherence and intervention arm, as described above. Stratification on these factors will allow for a diverse purposive sample that will include a range of types of young women who may have various experiences with PrEP use. Thus, we will conduct in-depth interviews at three time points with up to 25 young women or until saturation/redundancy are reached. We will also conduct debriefs with the qualitative interviewers and the counseling staff to explore their views on participant's experiences with the in-depth interviews and the interventions.

We will also interview approximately 10 key informants (e.g., PrEP program managers, health department staff) and 15 staff members to assess their perceptions of our intervention package and opinions on scalability of the interventions. We will also ask additional questions on their perceptions of providing more intensive psychosocial and mental health counseling services for AGYW in PrEP delivery settings to inform future counseling intervention work with this population. These questions are motivated by early findings from this study, and other recent PrEP projects in this setting, of a high need for mental health services and targeted psychosocial counseling around depressive symptoms, stress and anxiety, and gender-based violence and trauma among adolescent girls and young women seeking PrEP. Key informants will include individuals working on PrEP delivery, funding, policy, and/or implementation for AGYW in South Africa. Staff will include any doctors, nurses, recruitment officers, WhatsApp group facilitators, counselors, study coordinators, and other individuals with direct contact with AGYW at the clinic and engagement in PrEP delivery services. Key informant interview will assess: attitudes toward PrEP and mental health counseling for adolescent girls and young women and opinions of the inclusion of mental health care in PrEP delivery; opinions on needs for staff competencies and training and clinic supports for mental health and HIV service delivery; and potential contextual facilitators and barriers to integrating a mental health counseling intervention with PrEP delivery for South African adolescent girls and young women. Staff interviews will assess: experiences with PrEP delivery in the clinic; perceptions of PrEP SMART interventions; feelings of rapport with adolescent girls and young women; barriers to PrEP and counseling service delivery; satisfaction with clinic flow and suggestions for improvements;

attitudes toward PrEP and psychosocial and mental health counseling for adolescent girls and young women and opinions of the inclusion of further psychosocial support services in PrEP delivery; and potential facilitators and barriers to integrating a more intensive mental health counseling intervention with PrEP delivery for South African adolescent girls and young women. Interview guides will be semi-structured and based on the local literature and findings from PrEP SMART thus far. Trained researchers/ethnographers will conduct all interviews with oversight from the protocol team. All interviews will be audio-recorded and transcribed and translated into English by trained site staff.

In addition to data collection using in-depth interviews, we will also download SMS and WhatsApp messages and conduct a thematic content analysis of text messages to explore key themes around PrEP adherence, perceptions of the interventions, and participants' level of engagement with the SMS and WhatsApp services. At the end of each week, the WhatsApp discussion group moderator will export the content of the group chats from WhatsApp. The WhatsApp exports will initially contain identifiable patient information (phone numbers) and therefore will be protected with great care to ensure data security and avoid a breach of confidentiality. Site study staff will deidentify chats by permanently removing all phone numbers and names and replacing them with sequential study ID numbers. De-identified data will then be stored as a password protected file on a secure sever. We will follow a similar procedure to deidentify SMS data. Study staff will download the SMS data from the Telerivet platform on a weekly basis, permanently replace phone numbers and names with study ID numbers, and save deidentified data as a password protected file on a secure server. We will use descriptive statistics to summarize SMS and WhatsApp response rates and free-text SMS and WhatsApp responses will be analyzed using qualitative software methods.

4.4. PrEP

Participants will be provided with PrEP in the form of oral emtricitabine 200 mg / tenofovir disoproxil fumarate 300 mg (FTC/TDF) for once daily dosing. Prescriptions will be written as follows: 1 bottle at enrollment, 2 bottles at month 1, 3 at months 3 and 6. Bottles will be dispensed as follows: 1 bottle at each visit until month 3 and then 3 bottles at months 3 and 6. Participants will be directed to take PrEP once daily with or without food throughout follow up. If a participant forgets to take PrEP at the correct time, it may be taken later in the day; however, no more than one tablet should be taken on any calendar day.

4.4.1. PrEP Formulation, Content, and Storage

FTC/TDF is a fixed dose combination tablet containing 200 mg of emtricitabine (FTC) and 300 mg of tenofovir disoproxil fumarate (TDF) in each tablet. TDF/FTC was approved by the South African African Health Products Regulatory Authority (SAPHRA, formerly the Medicines Control Council) as PrEP in 2015.

FTC/TDF tablets (30 tablets/bottle) must be stored at 25°C (77°F), with excursions permitted to 15°C-30°C (59°F-86°F) (see USP Controlled Room Temperature). FTC/TDF tablets must be stored in the pharmacy in the original container.

4.5. Contraceptive Use and Pregnancy

Contraception use will be assessed at every study visit. Contraception counseling and provision will be offered at all study visits. For women who become pregnant, PrEP offers a strategy to reduce HIV risk in the peri-conception period, and data from PrEP clinical trials and demonstration projects have demonstrated that peri-conception use is safe in terms of pregnancy incidence, pregnancy outcomes, and infant outcomes.⁷⁵⁴

Current WHO guidance indicate that there is no safety-related rationale for disallowing or discontinuing PrEP during pregnancy and breastfeeding for HIV-negative women who are receiving PrEP and remain

at risk of HIV acquisition.⁷⁶⁵ The guidelines conclude that in such situations, the benefits of preventing HIV acquisition in the mother and the accompanying reduced risk of mother-to-child HIV transmission outweigh any potential risks of PrEP, including any risks of fetal and infant exposure to the drugs in PrEP regimens. Women who become pregnant while taking PrEP will be counselled about the benefits and risks of continuing during pregnancy, and allowed to continue PrEP if they choose.

4.6. Post-exposure prophylaxis

In the event of sexual assault or possible HIV exposure and if the participant reports inconsistent PrEP use, post-exposure prophylaxis (PEP) will be offered in accordance with local guidelines for one month. PrEP will be discontinued during the one month of PEP, and restarted following repeat HIV testing to exclude possible HIV seroconversion.

4.7. HIV Seroconversion

HIV testing will be performed at the following study visits – Enrollment, Month 1, and all quarterly visits. Participants who have at least one positive HIV rapid test will be instructed to discontinue PrEP immediately. Participants who have a positive HIV self-test at a remote visit will be requested to come to the research clinic for study staff to conduct additional HIV testing. All possible seroconverters will have locator information updated and will receive counseling. Blood will be collected and pregnancy testing will be conducted. HIV EIA, CD4, viral load, and genotypic resistance testing will be conducted in order to confirm seroconversion. In addition, a DBS and plasma sample will be archived for tenofovir testing. All other visit procedures corresponding to the study visit will also be conducted.

Participants with confirmed HIV infection will have one additional study visit, ideally within 1 month of the possible seroconversion visit at which time the participant will receive laboratory results. Confirmed seroconverters will permanently discontinue PrEP and the participant will be linked to a local HIV care clinic for appropriate follow-up and clinical management. All exit study visit procedures will be conducted and the participant will be permanently exited from the study.

4.8. Participant Retention

Participants will be in the study for 9 months of follow-up and retention procedures may include:

- Thorough explanation of the study visit schedule and procedural requirements during the informed consent process and re-emphasis at each study visit.
- Collection of detailed locator information at the Enrollment visit, and active review and updating of this information at each subsequent visit.
- Use of mapping techniques to establish the location of participant residences and other locator venues.
- Use of appropriate and timely visit-reminder mechanisms.
- Rapid and multi-faceted follow-up for missed visits.
- Mobilization of trained outreach workers or “tracers” to complete in-person contact with participants at their homes and/or other community locations.
- Regular communication with the study community at large to increase awareness about HIV/AIDS and explain the purpose of HIV prevention research and the importance of completing research study visits.

4.9. Participant Withdrawal

Participants may voluntarily withdraw from the study for any reason at any time. The site investigator also may withdraw participants from the study to protect their safety and/or if they are unwilling or unable to comply with required study procedures. Participants also may be withdrawn if the study sponsors, government or regulatory authorities, or site IRBs terminate the study prior to its planned end date.

Every reasonable effort will be made to complete final evaluations for participants who terminate from the study prior to the last study assessment or visit; study staff will record the reason(s) for all withdrawals from the study in participants' study records. Participant non-adherence to the intervention(s) or PrEP is not a reason for participant withdrawal from the study and we will continue to follow participants even if they decline the interventions (e.g., reply "STOP" to the two-way SMS messages) prior to the completion of follow-up.

5.0 SAFETY MONITORING AND ADVERSE EVENT REPORTING

5.1. Safety Monitoring

Close cooperation between the Protocol co-Chairs and other study team members will be necessary in order to monitor participant safety and to respond to occurrences of toxicity in a timely manner. The study investigators are responsible for continuous close monitoring and management of SAEs.

5.2. Adverse Event Definition and Reporting

For the purposes of this study, only serious adverse events (SAEs), creatinine clearance <60 ml/min, tolerability or side effects to PrEP that lead to discontinuation, and social harms associated with study participation will be recorded.

With appropriate permission of the participant, whenever possible, records from all non-study medical providers related to SAEs will be obtained and required data elements will be recorded on study CRFs. All participants reporting an AE will be followed clinically, until the AE resolves (returns to baseline) or stabilizes.

Site staff will also report information regarding SAEs to their IRB or other local regulatory agencies in accordance with all applicable regulations and local IRB requirements.

5.3. Relationship to PrEP

Relatedness is an assessment made by a study clinician of whether or not the event is related to PrEP. 'Not related' will be noted for SAEs among participants who discontinue PrEP.

SAEs will be defined as AEs occurring at any dose that:

- Result in death;
- Are life-threatening AEs;
- Require inpatient hospitalization or prolongation of existing hospitalization;
- Result in persistent or significant disability/incapacity; or
- Are congenital anomalies/birth defects.

Important medical events that may not result in death, be life-threatening, or require hospitalization may be considered serious when, based upon appropriate medical judgment, they may jeopardize the participant or require medical or surgical intervention to prevent one of the outcomes listed above.

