5.4. Creatinine Clearance

Creatinine clearance will be calculated using the Cockcroft-Gault Equation. If the calculated creatinine clearance is <60 mL/min, PrEP will be halted temporarily and creatinine testing repeated within two weeks. If renal function returns to normal ($\text{CrCL} \geq 60$ mL/min), PrEP may be re-started.

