5.5. Toxicity Management

The site investigator has the discretion to interrupt FTC/TDF at any time if s/he feels that continued medication use would be harmful to the participant or would interfere with treatment deemed clinically necessary according to the judgment of the investigator. Clinical or laboratory abnormalities that require follow-up will be documented, and the participant will be contacted to schedule an interim visit for follow-up and/or repeat laboratory testing if indicated. All participants reporting an adverse event (AE) Grade 3 or higher or any grade for creatinine will be followed clinically until the occurrence resolves (returns to baseline grade, defined as grade at Enrollment) or stabilizes. PrEP will be discontinued if the CrCl decreases below 60 ml/min and serum creatinine will be monitored. SAEs designated to be related to PrEP will result in temporary hold of PrEP. In the case of temporary holds, the hold will continue until the event is stabilized or resolved. In such cases, PrEP may be reinitiated at the discretion of the Investigator.

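### Section 5.3 labels SAEs 'Not related' because the woman discontinued PrEP, without regard to when the event began or why she stopped

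*Protocol*

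**What the plan says.** Protocol section 5.3 opens by leaving causality to individual judgement: "Relatedness is an assessment made by a study clinician of whether or not the event is related to PrEP". The next sentence sets a fixed outcome for one class of participant: 'Not related' "will be noted for SAEs among participants who discontinue PrEP". The list of SAE criteria that follows includes events that "Are congenital anomalies/birth defects".

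The neighbouring sections foresee PrEP being interrupted or stopped because of the drug:

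- Section 5.2 lists among the recorded safety items "tolerability or side effects to PrEP that lead to discontinuation".
- Section 5.5 states "SAEs designated to be related to PrEP will result in temporary hold of PrEP", and adds that after such a hold "PrEP may be reinitiated at the discretion of the Investigator".
- For creatinine clearance below 60 mL/min, section 5.4 says "PrEP will be halted temporarily and creatinine testing repeated within two weeks", while section 5.5 says "PrEP will be discontinued if the CrCl decreases below 60 ml/min and serum creatinine will be monitored".

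The SAP does not mention relatedness. It names SAEs only as a candidate predictor in Secondary Analysis 3.

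**The concern.** A causality label should rest on the event: when it began, what the exposure was, and what else could explain it. Section 5.3 rests it on whether the participant is a discontinuer. The most informative kind of related SAE, one serious enough to end treatment, falls inside that class.

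All participants are given FTC/TDF, so no PrEP-free arm exists whose SAE rate could expose a drug effect. Case-level attribution therefore carries more weight than it would in a placebo-controlled trial. The monitoring committee reviews SAEs about every six months (section 8.3), and site staff report SAEs to the IRB or other local regulatory agencies (section 5.2). A label fixed by rule could mislead these readers about which events were thought to be caused by the drug.

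**Working it through.** The plan states no SAE rate, no count of related SAEs and no figure based on relatedness, so there is nothing to reproduce. The check is textual.

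**Step 1: scope of the rule.** The wording is mandatory and covers participants who discontinue. It does not mention onset date, last-dose date or reason for stopping. Nothing elsewhere in the protocol or SAP narrows it.

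**Step 2: apply it to the possible cases.** The literal reading covers any SAE in a woman who discontinues. The narrow reading covers only SAEs that begin after she has stopped.

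| Case | Literal reading | Narrow reading |
|---|---|---|
| Onset on PrEP, held under 5.5, restarted | Clinician decides | Clinician decides |
| Onset on PrEP, leads to permanent discontinuation | 'Not related' by rule | Clinician decides |
| Onset on PrEP, woman later stops for another reason | 'Not related' by rule | Clinician decides |
| Onset or detection after stopping, tied to earlier exposure (e.g. birth defect) | 'Not related' by rule | 'Not related' by rule |
| Onset after stopping, no link to exposure | 'Not related' by rule | 'Not related' by rule |

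The rule does no harm in the last row. It overrides judgement in three rows under the literal reading and in one under the narrow reading. The birth-defect case is foreseeable, because section 4.5 lets women who become pregnant choose to continue PrEP.

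**Step 3: the boundary of 'discontinue'.** The first row is safe only if a hold is not a discontinuation. Restart after a hold is discretionary, so a hold can become permanent. For the same creatinine-clearance threshold, section 5.4 describes a temporary halt and section 5.5 a discontinuation. Whether section 5.3 reaches an SAE in such a woman depends on which section is followed.

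**Step 4: form of the undercount.** Let *f* be the share of truly related SAEs that the rule reaches. Then

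recorded related SAEs = (1 − *f*) × true related SAEs.

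The documents give no value for *f*. Taking illustrative values purely as assumptions:

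- *f* = 0.25: 1 − 0.25 = 0.75, so 25% are lost.
- *f* = 0.50: 1 − 0.50 = 0.50, so 50% are lost.
- *f* = 1.0: 1 − 1.0 = 0, so all are lost.

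**The case against.** The strongest reply is that the authors meant women already off PrEP when the SAE occurs. The order of events in section 5.5 supports this: the relatedness designation comes first and the hold follows. An on-drug SAE would then be assessed before PrEP was stopped because of it, and no section tells staff to recode it afterwards. This makes the narrow reading plausible, and it rules out saying that every such SAE will be miscoded. It does not settle the matter. The text does not state the narrow reading, and nothing fixes the label at first assessment. SAEs are scheduled for assessment at month 1 and the quarterly visits, so a woman treated elsewhere who has already stopped may first be assessed as a discontinuer. The narrow reading also leaves the birth-defect case.

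It is also fair to say that the consequence is limited. Every SAE is still recorded, reported and reviewed whatever its label. Side effects that end treatment are a separate recorded item. No objective is a safety objective, and neither document specifies an analysis of related SAEs. All of this stands.

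Two stronger inferences are tempting and should be resisted:

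- A reader might gauge the rule's reach from the planned fall from up to 500 enrolled to about 350 analysed (section 6.3), or from the cited detectable-tenofovir figure below 50% between months 3 and 6 (section 1.2.1). The first concerns return and continuation; the second is adherence in another study. Neither counts SAEs in women who discontinued.
- A reader might treat the 4–6 weeks of dosing reflected by TFV-DP as a window for drug-related harm. The protocol presents it only as an adherence measure.

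**Conclusion.** The point holds as a defect in one stated rule. As written, section 5.3 lets discontinuation alone determine causality, contradicts the clinician assessment in the preceding sentence, and would label as unrelated an SAE that began on PrEP and ended treatment. Under the narrower reading the main harm disappears, but the text remains unclear and events tied to earlier exposure are still labelled by rule.

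The damage is confined to the causality label and the related-SAE count. Its size cannot be derived from the documents, and the shares in the working are assumptions. The conclusion rests on two premises: that staff code what the sentence says, and that no instruction outside these documents narrows it. The correction is worth making because it is cheap and improves the safety information sent to the monitoring committee and ethics bodies.

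**What to change.** 1. Delete the automatic sentence from section 5.3, so that the study clinician assesses relatedness for every SAE and discontinuation alone never sets the code. Limiting the sentence to SAEs that begin after stopping would be a smaller edit, but it would leave the birth-defect case.
2. Base the assessment on the SAE's onset date and the date of the last PrEP dose. Add these to the CRF if they are not already collected; the CRFs are not among the documents.
3. Re-review any SAE already coded under the rule.
4. Reconcile the terms for a hold, a temporary halt and a discontinuation across sections 5.2 to 5.5, including the creatinine-clearance text in 5.4 and 5.5. Which clinical rule should apply is for the investigators to decide.

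The cost is one deleted sentence, a terminology edit in four short sections, at most two date fields, and a review confined to SAE forms from women who discontinued. No endpoint, sample size or planned analysis changes.
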